5.4. Drug Accountability

Full drug accountability will be maintained.

The pharmacy clinical trials team will maintain full accountability records of the IMP. The pharmacy accountability logs will capture details of the subject to whom the investigational medicinal product was dispensed/prepared, the date, batch number, expiry date and quantity of the investigational product received, dispensed and unused.

5.5. Storage of IMP

IMP will be stored in the clinical trials pharmacy at King's College Hospital, according to the SmPC requirements. Both edoxaban and rivaroxaban do not require any special storage conditions and thus will not require temperature monitoring. The IMP will be stored under local hospital policy.

5.6. Participant Compliance

Subject's compliance with medication will be monitored by direct and real-time observation by the research team. The date and time of administration will be recorded.

5.7. Concomitant Medication

For management of concomitant therapies, please refer to the edoxaban and rivaroxaban Summary of Product Characteristics. A complete listing of all concomitant medication received during the treatment phase must be recorded in the relevant CRF.

Use of the following agents (prescription or non-prescription) presented in Table 5-4 and 5-5 is prohibited from the time points specified until completion of all study activities. More details are in the SmPC of edoxaban and rivaroxaban.

In the interests of subject safety and acceptable standards of medical care the Investigator will be permitted to prescribe treatment(s) at his/her discretion. All treatments must be recorded in the subjects' CRF (medication, dose, treatment duration and indication).

Table 5-4 Restricted Medications in EDX group of the Study

72 Hours Prior to Admission	24 Hours Prior to Admission
Prescription medications including anticoagulants and antiplatelet aggregation medicinal products; Significant CYP3A4 inhibitors and inducers; Significant P-gp inhibitors and inducers.	Nutraceuticals (e.g., St. John's Wort, ginseng, kava kava, Ginkgo biloba and melatonin)
Non-steroidal anti-inflammatory drugs (aspirin, ibuprofen, diclofenac, naproxen, indomethacin).	Foods or beverages containing Seville-type (sour) oranges, or poppy seeds

Table 5-5 Restricted Medications in RVX group of the Study

72 Hours Prior to Admission	24 Hours Prior to Admission
Prescription medications including anticoagulants and antiplatelet aggregation medicinal products; Significant P-gp inhibitors and inducers; Significant CYP3A4 inhibitors and inducers.	Nutraceuticals (e.g., St. John's Wort, ginseng, kava kava, Ginkgo biloba and melatonin)
Non-steroidal anti-inflammatory drugs (aspirin, ibuprofen, diclofenac, naproxen, indomethacin).	Foods or beverages containing grapefruit, seville-type (sour) oranges, or poppy seeds

6. Selection and Withdrawal of Participants

6.1. Inclusion Criteria

To be eligible to participate in this study all the following criteria must be met:

1. Subject is informed and given ample time and opportunity to think about her participation and has provided written informed consent for participation in the study before any study specific procedures take place.
2. Subject is considered reliable and capable of adhering to applicable protocol requirements, including the study drug being administered orally and visit schedule according to the judgement of the Investigator.

3. Women are aged ≥ 18 years.
4. Within the 12 weeks postpartum period.
5. Decision has been confirmed by the volunteer to hold breastfeeding their infant during the study period.
6. Negative pregnancy test.
7. Good physical and mental health, in the opinion of the investigator, determined on the basis of medical history and general clinical examination at screening.
8. Women have clinical laboratory test results within the reference ranges of the testing laboratory: normal renal and liver function, as judged by the chief investigator.
9. Women are not taking any medication interacting with edoxaban or rivaroxaban, as listed in table 5-4 and 5-5.
10. Women are available and permit the research team to make home visits to collect blood and milk samples.
11. Women agree to the study restrictions, as outlined in section 6.3.

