4.5. Trial Flowchart

[figure not shown]
Table 4-1: Trial procedures during the clinical trial – EDX and RVX groups

	Pre-sampling		Sampling								Post-sampling		
	Screening	Randomisation	Visit 1 (day 1)				Visit 2 (day 2)	Visit 3 (day 3)				Final Visit (day 6)	
			0 hr	3 hr	12 hr	24 hr	0 hr	0 hr	3 hr	12 hr	24 hr		
Written informed consent	X												
Patient demographics	X												
Eligibility assessment, including vital signs	X	X											
Past medication, medical and social history	X												
Bloods (UEs, LFTs, FBC, coag screen) – safety bloods	X												X
Pregnancy test	X												
Randomisation (if applicable)		X											
Bloods reviewed and volunteer given all clear to take part. Date arranged with volunteer to do the study sampling		X											
IMP dispense		X											
Vital signs and then IMP administration			X				X	X					
Milk sampling (+/- 30min)				X	X	X		X (pre-dose)	X	X	X	X	X

Pharmacokinetic blood samples				X	X	X		X (pre-dose)	X	X	X	X
Adverse events			X	X	X	X		X	X	X	X	X
End of trial for patient												X

Figure 4-1. Milk and blood collection time points – EDX and RVX groups

[figure not shown]
DAY 1

DAY 2

Second dose of EDX / RVX administered.

DAY 3

DAY 6

72 hours post day 3 dose.

5. Trial Medication

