5.2. Dosing Regimen

The study drug will be orally administered as tablet (edoxaban or rivaroxaban) formulation once a day on days 1, 2 and 3. The IMP will be administered at subject’s home under the guidance of the investigator with the date and time of administration recorded in the subject’s CRF.

Table 5-3 Dosing regimen

Study Arm	Study Drug Dose	Subjects	Duration for each subject* (Day -28 to day 6)		
Edoxaban (EDX)	60 mg (once daily)	6	Screening (day -28 to -3)	Treatment (day 1 to 3 inclusive)	Safety review (day 6) & study closure
Rivaroxaban (RVX)	20 mg (once daily)	6		Treatment (day 1 to 3 inclusive)	

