6.8. Expected Duration of Trial

The beginning of the trial will be defined as first patient first visit and the end of trial will be defined as database lock.

Active participation in the trial for each volunteer is for 6 days and each individual participant will remain on trial until the morning of day 6 - final visit.

7. Trial Procedures

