7.1.1 Screening Visit

The following study evaluations will be performed/recorded during the course of the screening period (28 days):

- Signed informed consent
- Inclusion and exclusion criteria
- Record past medical and social history
- Record of concomitant medication usage, including contraindicated/restricted medication
- Participant demographics
- Pregnancy test
- Blood sampling (safety bloods)
- Vital signs

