7.1.2 Day 1 (0hr)

- Record of concomitant medication usage, including contraindicated/restricted medication
- Vital signs
- IMP administration

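### The only pregnancy test is at screening, so the negative result is 3 to 28 days old at the first anticoagulant dose and no repeat is required

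*Protocol*

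**What the plan says.** - **Criterion.** Section 6.1, criterion 6, reads "Negative pregnancy test". It gives no date or interval relative to dosing.
- **Schedule.** Table 4-1 (section 4.5) marks the pregnancy test once, under Screening. Section 7.1.1 lists it there and nowhere else. The lists for Days 1, 2, 3 and 6 (sections 7.1.2 to 7.1.6) do not contain it. The Day 1 0 hr list has a medication check, vital signs and dosing.
- **Sample count.** Table 7-1 (section 7.2) counts one pregnancy sample of 3.5 mL within the blood total.
- **Timing.** Table 5-3 (section 5.2) puts screening at day -28 to -3. Dosing is on days 1, 2 and 3, in the volunteer's home, "under the guidance of the investigator with the date and time of administration recorded".
- **Second eligibility check.** The Table 4-1 row "Eligibility assessment, including vital signs" is marked at Screening and again at Randomisation. The pregnancy-test row has no second mark.
- **Contraception.** Exclusion 11 (section 6.2) bars pregnant women, and women of childbearing potential who refuse effective contraception for the duration of the study. Its start is not defined. Table 5-3 gives each subject's duration as day -28 to day 6, while section 6.8 says "Active participation in the trial for each volunteer is for 6 days".

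**The concern.** The protocol treats pregnancy as a safety matter: it excludes pregnant women, requires a negative test, and sends any unplanned pregnancy through the SAE reporting system (section 8.2). The participants are healthy mothers who take full-dose anticoagulants for pharmacokinetic purposes only. Medication and vital signs are checked again just before the first dose. Pregnancy status, which can also change after screening, is not. A team that follows the plan exactly may dose on a result four weeks old. Because no later visit includes a test, a pregnancy missed at screening has no scheduled means of detection during the trial.

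What is at stake is participant safety and the currency of an eligibility criterion. The sample size and the pharmacokinetic analysis are not affected.

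**Working it through.** **1. Is there really only one test, and is it a blood sample?** The blood rows of Table 7-1 give

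5.0×2 + 3.7×2 + 2.0×2 + 3.5×1 + 2.0×8 = 10.0 + 7.4 + 4.0 + 3.5 + 16.0 = 40.9 mL,

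which rounds to the stated 41.0 mL. Without the pregnancy sample the sum is 37.4 mL; with two such samples it is 44.4 mL. The stated total therefore contains exactly one pregnancy test, taken as blood.

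**2. Age of the result at the first dose (S).** With no day 0, day -3 to Day 1 is 3 days and day -28 to Day 1 is 28 days. If a day 0 is counted, the range is 4 to 29 days. The protocol does not say which applies, and the point is the same either way.

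**3. What a Day 1 urine test would add.** The protocol gives no detection times, so these are assumptions:

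- L = 10 to 14 days from conception to a positive blood test.
- x = 0 to 4 further days before urine turns positive.
- D = days from delivery to the first dose. Conception cannot precede delivery. I use D = 84 (the 12 weeks of criterion 4, 12×7) and D = 35 as an illustration. Any D of 42 or more gives the D = 84 results, because S + L is at most 28 + 14 = 42.

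The screening test misses conceptions in the last min(D, S+L) days before the dose. A Day 1 strip misses those in the last min(D, L+x) days. The gain is the number of conception days missed at screening but caught on Day 1.

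- Reading (a), contraception from screening and taken as fully effective, so that only conceptions at least S days before the dose count: gain = max(0, min(D, S+L) − max(S, min(D, L+x))).
- Reading (b), contraception from Day 1 only: gain = max(0, min(D, S+L) − min(D, L+x)).

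| D | S | Gain under (a) | Gain under (b) |
|---|---|---|---|
| 84 | 3 | 3 − x, not below 0: 0 to 3 days | 3 − x, not below 0: 0 to 3 days |
| 84 | 28 | (38 to 42) − 28 = 10 to 14 days | 28 − x = 24 to 28 days |
| 35 | 28 | 35 − 28 = 7 days | 35 − (10 to 18) = 17 to 25 days |

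These are counts of days, not probabilities.

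**4. Do other provisions require a repeat?** The second eligibility mark at Randomisation comes without a second pregnancy-test mark. The extra samples allowed in section 7.2 are at the investigator's discretion. Exclusion 11 is a preventive rule, not a test.

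**The case against.** The strongest case is that the plan is coherent as written. Table 4-1, section 7.1.1 and Table 7-1 agree with one another, and the schedule supplies the timing that criterion 6 leaves out. The gap between screening and dosing already has a control in exclusion 11. The natural reading is that contraception runs from screening, since Table 5-3 starts each subject's duration at day -28 and section 6.8 dates the trial from the first patient's first visit. The larger gains (24 to 28 and 17 to 25 days) then fall away. Under reading (a) the gain is zero when D is 28 or less with screening on day -28, and the 7 days at D = 35 are all in the first week after delivery. The calculation weights every day since delivery equally, with nothing to support that. Day -28 is the edge of the window and need not be typical. Finally, a Day 1 strip cannot exclude a very recent conception, so the trial would still depend on contraception.

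Much of this stands. Nothing is contradicted, reading (a) is the more natural, the reading (b) figures are best taken as an upper bound, and the benefit may be nil for late screening. What does not follow is that the gap is closed. Contraception does not detect its own failure, and it cannot act on a conception shortly before a screening test that was still negative. Under reading (a) that second group alone accounts for the 10 to 14 days.

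**Conclusion.** The concern holds. One blood pregnancy test is planned, at screening, and no later step requires another, so the result is 3 to 28 days old at the first dose. Under the assumed detection times, a Day 1 test would extend detection by 10 to 14 conception days for a woman screened on day -28 and dosed late in the 12 weeks, if contraception starts at screening. The figure is 24 to 28 days if contraception starts only on Day 1. It is smaller soon after delivery, and 0 to 3 days for screening on day -3.

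The absolute risk is low: 12 women, three doses each, contraception required. The protocol gives no fetal-harm figure, and neither that nor a probability of pregnancy is claimed here. This is an inexpensive safety improvement that should be made; no endpoint or analysis depends on it.

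**What to change.** 1. Add a urine pregnancy test, negative before IMP is given, to the Day 1 0 hr column of Table 4-1 and to section 7.1.2.
2. State in section 6.1 that criterion 6 must hold at screening and again on Day 1 before the first dose.
3. Keep exclusion 11 and say that contraception starts at screening. No Day 1 strip can exclude a conception in the last 10 to 18 days (L + x, assumed), so contraception remains the control for that period.

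The cost is about 12 urine strips at a home visit already made for observed dosing, and a short amendment. No extra blood is needed; even a repeat blood test would bring the total only to 44.4 mL, against the 100 mL ceiling in section 7.2. The downside is an occasional late screen failure, in a woman the protocol already means to exclude.

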6.2. Exclusion Criteria

Subjects are not permitted to enrol in the study if any of the following apply:

1. Low Molecular Weight Heparin (LMWH) thromboprophylaxis is indicated.
2. Increased risk of bleeding for any reason.
3. Known contra-indications to edoxaban or rivaroxaban.
4. On-going treatment with aspirin, NSAIDs (ibuprofen, diclofenac, naproxen, indomethacin) or other drugs that affect haemostasis.
5. Treatment with significant P-GP / CYP3A4 inducers or inhibitors.
6. Patients who have received an artificial heart valve, have had a heart attack or suffer an irregular heartbeat.
7. Known impaired renal function.
8. Known abnormal liver function tests.
9. Known hypersensitivity or allergy to edoxaban or rivaroxaban.
10. Use of other investigational study drugs within 7 days prior to study entry.
11. Women who are pregnant or of childbearing potential who refuse to use an acceptable effective form of contraception throughout the study. Acceptable forms of contraception include: combined (estrogen and progestogen containing) hormonal contraception associated with inhibition of ovulation (oral, intravaginal, transdermal), progestogen-only hormonal contraception associated with inhibition of ovulation (oral, injectable, implantable) intrauterine device (IUD), intrauterine hormone-releasing system (IUS), bilateral tubal occlusion, vasectomised partner, sexual abstinence.
12. Women who will not participate in study visits within a suitable distance from King's College Hospital NHS Foundation Trust, as judged by the research team.

6.3. Study Restrictions

Subjects must be willing and able to adhere to the following prohibitions and restrictions during the course of the study:

Refrain from intake of grapefruit juice from 48 hours prior to dosing and until 24 hours post last dose of IMP;

Refrain from taking drugs of abuse during the study;

Refrain from taking medications during the study as outlined in Section 5.7;

Refrain from breastfeeding their infant during the study.

6.4. Selection of Participants

Participants will be recruited from an advertisement on www.mums.net, local mum's forums, and the outpatient clinic letters at the Hematology department of King's College Hospital NHS Foundation Trust. Volunteer women will be given £300 as a thank you for their time and participation. Should subjects fail at the screening they will receive reimbursement for their travel (up to £10). Subjects who voluntarily withdraw or are withdrawn from the trial on clinical grounds (CI decision), will receive 'part-payment' for their participation to the point of their involvement. This part-payment will be calculated on the basis of the number of pairs of breastmilk and plasma samples contributed by the volunteer. Each pair of samples contributed by volunteers will be paid £37.50p.

6.5. Consent

Volunteers will initially contact [name] to express interest in taking part. A phone call will be arranged, where the trial PIL will be explained to the potential subject and any preliminary questions answered. The volunteer will then be encouraged to discuss with family / friends. Following a minimum of 24 hours, if the volunteer would like to proceed to screening, then a screening visit will be arranged, where the study information will be repeated and questions answered and bloods drawn. If patient is deemed suitable to take part following review of bloods, written informed consent will be obtained, following all the principles of Good Clinical Practice (GCP), and the Declaration of Helsinki.

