7.1. By Visit

Each participant will have pre-entry screening. For practical reasons, this may be conducted at the subject's home. Each home visit for the purposes of the trial will be conducted by a researcher and a chaperone. Following informed consent for the study has been obtained, the research team will check her medical history and physical health (including vital signs), as well as ask volunteers to have screening bloods. The procedures during each visit are detailed in Table 4-1.

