7.2. Laboratory Tests

According to the milk and blood collection time points and safety assessment schedule, the blood and milk volumes to be collected from any single subject are presented in Table 7-1.

Blood samples will be packed and transferred to King's College Hospital immediately after collection. Clinical samples (UEs/LFTs/FBC) will be handled by the Viapath, King's College Hospital. Pharmacokinetic blood samples will be cooled and centrifuged as soon as possible in the CI's laboratory at King's College Hospital. The separated plasma samples will be transferred to a clean tube and stored at -20°C.

Milk samples will be stored at -20°C in the CI's laboratory at King's College Hospital. Separated plasma samples and milk samples will then be transferred to ASI Bioanalytics (London, UK) within 56 days for the analysis. Detailed sample collection, handling, labelling, storage and shipment will be described in the Laboratory Manual at King's College Hospital and ASI Bioanalytics.

Table 7-1 Blood and Milk Volumes to be Collected in a single subject in EDX/RVX group over the course of the volunteers involvement in the trial

Assessment	Sample Volume (mL)	No. of Samples	Total Volume (mL)
Safety			
Clinical Chemistry	5.0	2	10.0
Haematology (PT, APTT)	3.7	2	7.4
FBC	2.0	2	4.0
Pregnancy test	3.5	1	3.5
Pharmacokinetic			
Plasma Samples	2.0	8	16.0
Milk Samples	10.0	8	80.0
Total (mL)			Blood: 41.0 Milk: 80.0

FSH: Serum Follicle-stimulating Hormone

Sample volumes are based on direct venepuncture.

Milk sample to be collected at any breast (10ml) by manual expression or breast pump.

Additional samples may be collected as required at the Investigator's discretion. However, the total volume of blood collected per subject during the study will not exceed 100 ml. Individual venepunctures for each time point will be performed. The exact date/time of the milk and blood sample collection will be recorded in the subject's CRF.

Time windows for the collection of the PK blood and milk samples are as follows:
±30 minutes for all sampling time points (with the exception of the pre-dose sample).

8. Assessment of Safety

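### Section 6.5 takes written consent only after the screening bloods are drawn and reviewed, which contradicts inclusion criterion 1 and section 7.1

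*Protocol*

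**What the plan says.** Section 6.5 (Consent) sets out a sequence. A phone call explains the information leaflet and at least 24 hours follow. If the woman wishes to proceed, "then a screening visit will be arranged, where the study information will be repeated and questions answered and bloods drawn". The next step is "If patient is deemed suitable to take part following review of bloods, written informed consent will be obtained". No earlier or separate consent for screening is described.

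Other parts of the protocol read differently:

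- Section 6.1, inclusion criterion 1: the woman "has provided written informed consent for participation in the study before any study specific procedures take place".
- Section 7.1: "Following informed consent for the study has been obtained, the research team will check her medical history and physical health", and, in the same sentence, "as well as ask volunteers to have screening bloods".
- Section 7.1.1: the first item listed for the 28-day screening period is "Signed informed consent"; the pregnancy test and safety bloods appear further down the list.
- Section 4.5, Table 4-1: written consent and safety bloods are both marked under Screening. The row "Bloods reviewed and volunteer given all clear to take part" is marked under Randomisation, the next column, where no consent is marked.

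**The concern.** Section 6.5 makes written consent depend on the blood results, so it cannot come before the blood draw. Criterion 1 and section 7.1 require the reverse. The conflict sits in the section headed Consent, which is where site staff, monitors and the ethics committee would look for the process.

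What is at stake is participant protection. Under section 6.5 a volunteer has blood taken for the study, and the results reviewed, before she has signed anything. If her results rule her out, she never signs at all. A woman who is enrolled by this route has also not met the protocol's own first inclusion criterion.

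**Working it through.** The question is one of order, so the check is to set the sections side by side.

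| Place in the protocol | Position of written consent | Explicit order against the blood draw? |
|---|---|---|
| 6.5 Consent | After the bloods are drawn and reviewed | Yes: consent after |
| 6.1, criterion 1 | Before any study-specific procedure | Yes: consent before |
| 7.1 By Visit | Before history, physical check and screening bloods | Yes: consent before |
| 7.1.1 Screening Visit | First item in the list | No: the list states no order |
| Table 4-1 | Screening column, the same as safety bloods | No, but review of bloods is one column later |

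**Are the screening bloods study-specific?** Yes. Section 4.4 describes the volunteers as healthy breastfeeding mothers, and section 6.4 recruits them by advertisement, forums and clinic letters. The protocol gives no clinical-care reason for the tests. They appear in the trial schedule (Table 4-1) and in Table 7-1, titled "Blood and Milk Volumes to be Collected in a single subject in EDX/RVX group over the course of the volunteers involvement in the trial". Criterion 1 therefore covers them.

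**Can the sections be reconciled as they stand?** Section 6.5 runs draw, review, consent. Section 7.1 runs consent, draw. Both cannot hold for the same woman. Table 4-1 does not order consent against the draw, but it does put the review of bloods later than consent, which section 6.5 reverses. So two places contradict section 6.5 on the draw, one contradicts it on the review, and none supports it.

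**Volume of blood involved.** Table 7-1 does not label any sample as a screening sample, so this is an inference. Table 4-1 marks safety bloods at screening and at the final visit, which matches the two samples of each type in Table 7-1, and it marks the pregnancy test at screening only. Taking one of each pair plus the pregnancy sample:

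- clinical chemistry 5.0 mL + PT/APTT 3.7 mL + FBC 2.0 mL + pregnancy test 3.5 mL = 14.2 mL
- without the pregnancy sample: 14.2 − 3.5 = 10.7 mL

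As a check on reading the table, its blood rows sum to 10.0 + 7.4 + 4.0 + 3.5 + 16.0 = 40.9 mL against a stated 41.0 mL, a rounding difference.

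**How many women?** All who are screened by the section 6.5 route: the 12 planned participants plus an unstated number of screen failures.

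**The case against.** The best defence is that the protocol states the right order elsewhere. Staff who work from criterion 1 or section 7.1 would take consent first, and nobody would be bled beforehand. Section 6.5 also ensures that the woman is informed: an explanation by phone, at least a day to reflect, the information repeated and questions answered at the visit. Both points are fair and they limit the claim. The consequence is conditional on staff following section 6.5, and what is missing is written consent, not information. Neither point removes the contradiction, because criterion 1 asks specifically for written consent.

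Three stronger readings are tempting and are not supported:

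- A reader might infer that women will be bled without any consent. The documents show only that one section directs staff to draw blood before written consent, while others direct the opposite.
- A reader might infer that the data would be compromised, for example that each enrolled woman carries a major deviation, or that losing one of 6 in an arm costs 17% of it (1/6). The protocol neither classes late consent as a major deviation nor has a rule excluding data on that ground. Section 6.7 says only that a subject may be withdrawn for a protocol violation. Even under section 6.5, written consent comes before dosing and before every milk and plasma sample.
- A reader might cite section 7.1.1 and Table 4-1 as placing consent before the blood draw. They do not settle that order; only criterion 1 and section 7.1 do.

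Nor does the 14.2 mL measure added harm: the same blood would be drawn from a woman who consents first. It shows only how much would be taken before she signs.

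**Conclusion.** The contradiction is real and needs correcting before the protocol is used. Section 6.5 places written consent after the blood draw and its review, against criterion 1 and section 7.1, and out of line with Table 4-1 on the review. If section 6.5 is followed, study blood of about 14.2 mL (10.7 mL if the pregnancy sample is not taken then) comes from every screened woman without written consent, and the enrolled women fail criterion 1.

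This rests on two assumptions: that the bloods named in section 6.5 are the screening safety bloods of Table 4-1, and that Table 7-1 divides its paired samples between screening and the final visit. The contradiction itself does not depend on the volume. The weight of the point comes from participant protection and consistency alone.

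**What to change.** Reword section 6.5 so that written informed consent is obtained at the start of the screening visit, after the information has been repeated and questions answered, and before any blood is drawn or any other study procedure begins. Then state that the review of bloods confirms eligibility and leads to the arrangement of a sampling date, as Table 4-1 already shows; it should not trigger consent. It would help to say in section 7.1.1 that consent precedes the other screening items, since the list now leaves the order open.

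The cost is a change of a sentence or two in one section, and one clause if section 7.1.1 is also clarified. No visit, dose, sampling time or analysis changes. The one downside is that women who later fail screening will also have signed a consent form, and those forms must be kept.
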